2.2.2 Liver SBRT

Stereotactic Body Radiotherapy (SBRT) has increasingly been shown to have an important role in the treatment of HCC.

Historically conventional external beam radiation to the liver was associated with radiation induced liver toxicity (RILD). Classic RILD refers to a syndrome characterized by anicteric hepatomegaly, elevation of liver enzymes (ALP>AST) and ascites and can progress to liver failure, despite maximal care. Classic RILD is uncommon in modern radiation therapy series, when the dose to the liver can be kept below recommended levels. Technological advances in radiation treatment planning, breathing motion management and image guided radiation therapy (IGRT), have made it possible for ablative doses of

radiation to be delivered safely to focal unresectable HCC, using conformal RT, SBRT or protons. However, a decline in liver function (e.g. as assessed using Child Pugh score or ALBI) 3 months following radiation therapy is seen in 10 – 30 % of patients. Presence and progression of main portal branch HCC may contribute to this, and subsequent improvement in liver function often follows if the vascular HCC responds to radiation therapy (which may be delayed at 3 – 6 months post radiation).

SBRT involves the delivery of high doses of RT in smaller fractions using highly precise techniques therefore minimizing injury to surrounding hepatic parenchyma. Furthermore, cell death may be enhanced by causing vascular injury together with double-strand DNA breakage.

SBRT for the treatment of unresectable HCC was first reported in 1995 and recent studies predominantly in patients with tumors < 6 cm have demonstrated high local control rates of 70 - 90% at 1-2 years.²⁵⁻³⁰ In one study of 38 HCC patients previously treated with TACE, 33 – 57 Gy was delivered in 3 fractions, with a 61% 2 year survival.²⁹ Doses > 42 Gy in 3 fractions were associated with improved local control. In another study of 48 patients with HCC treated with 3-fraction SBRT (30 – 39 Gy), 11% of patients had a decline in Child-Pugh class, which was more likely if less volume of liver was spared (<800 cc of liver receiving 18 Gy or more).³¹ Early studies in Japan have reported survival at 1 year of 99% and 100% in patients with small tumors treated with SBRT, suggesting a potential curative role in this select population.^{32,33}

In patients with more advanced HCC, SBRT has also been used successfully. However, individualization of the SBRT dose is required to reduce the risk of toxicity. Interestingly, even non-ablative SBRT doses have been associated with long term control of the irradiated locally advanced HCC, and recanalization of the vascular HCC has been observed.³⁴ Xi et al reported a 50% one year survival in 41 patients with vascular HCC following 30 – 48 Gy in 6 fractions.³⁵

An iso-toxic RT schedule that allows patients with HCC unsuitable for standard therapies to be treated in 6 fractions over two weeks using SBRT was developed at Princess Margaret Hospital (PMH), University of Toronto.³⁶ The dose per fraction was determined based on the effective volume of normal liver irradiated (Veff), accounting for differences in dose per fraction. When the effective liver volume irradiated was low (Veff < 25%), doses of 54 Gy (9 Gy x 6) were delivered safely to HCCs, with excellent local control. For patients requiring higher volumes of liver to be irradiated (Veff 25-80%), doses from 24 to 54 Gy (4 to 9 Gy x 6) were delivered safely, although local control was reduced. An analysis of the completed phase I and II Toronto SBRT studies of 102 Child-Pugh A HCC patients ineligible for local-regional therapies (38% Hepatitis B, 38% Hepatitis C, 25% alcohol; 55% portal vein thrombosis; 12% extrahepatic disease) treated with SBRT (median dose 36 Gy in 6 fractions) from 2004 to July 2010 found a median survival of 17.0 months and 1 year local control rate of 87%. A dose response for local control was observed, with more sustained local control when 30 Gy in 6 fractions or more was delivered.³⁴ No classic RILD was seen. However, a decline in Child Pugh score was seen in approximately 30% of patients 3 months following SBRT. Factors significantly associated with toxicity were baseline Child Pugh score (A6 versus A5), lower baseline platelet count, mean liver (minus HCC volume) dose, and dose to 800cc of liver (minus HCC volume, D800cc). There was no toxicity if the mean liver dose (MLD) was < 18 Gy in 6 fractions and the D800cc was < 15 Gy in 6 fractions.³⁷ In 2012, at Princess Margaret Cancer Centre, a change from 6 fraction SBRT was made to 5 fraction SBRT, and 5 fraction SBRT is now our clinical standard of care and is the SBRT fractionation being tested in a phase III randomized trial (RTOG1112 - <https://clinicaltrials.gov/ct2/show/NCT01730937>).

In summary, although local control (including sustained stable disease) is likely with modest dose SBRT, even to large HCCs or those associated with vascular invasion, progression outside the irradiated volume is common following SBRT alone (PFS ~ 3-4 months), and there is rationale to combine SBRT with systemic therapies.

2.2.3 Combination of SBRT and pembrolizumab

There is significant biologic rationale for synergy between radiotherapy and immunotherapy, as SBRT may provide an immunologic “adjuvant” for use with checkpoint blockade.^{38,39} Early phase II data of combination ICI and radiation in melanoma are promising.⁴⁰ Preclinical data suggests that higher doses per fraction, as used with SBRT, are more likely to induce an immune response and abscopal effect.⁴¹⁻⁴³ The abscopal effect has been seen in several tumor types, including renal cell carcinoma, melanoma and anecdotally in several patients with HCC.⁴⁴⁻⁴⁷ The combination strategy of ICI and SBRT in HCC has the advantage of inducing locoregional response in liver and vascular disease as well as targeting extrahepatic metastases. A recent orthotopic murine model of HCC has demonstrated the superiority of combination SBRT and anti-PD-1 blockade compared to either modality alone.⁴⁸ Other pre-clinical models of combinations SBRT and immune checkpoint blockade have revealed similar results with the abscopal effect only elucidated when immunotherapy was added.^{43,49} A mouse model in GBM also evaluated sequence of treatment and a number of clinical studies have demonstrated both in field and abscopal responses to combination therapy.⁵⁰⁻⁵⁴ Although the most optimal sequencing of treatment is not clear, concurrent treatment appears superior in murine models.^{48,55,56}

There is no clinical experience with the combination of anti-PD-1 blockade and SBRT for liver cancer and limited experience with combined check point inhibitors and radiation therapy for any type of cancer. A retrospective study of 127 patients with melanoma treated with ipilimumab and local therapy reported better local control, survival and increased abscopal effects in patients treated with local therapy in addition to ipilimumab, with no increase in toxicity in patients treated with local therapies.⁵⁷ The majority of patients received radiation therapy to the brain, the skin or lymph nodes, with 2 receiving radiation therapy to the liver.

A phase III study of 799 patients treated with palliative radiation therapy (8 Gy in 1 fraction) for bone metastases from prostate cancer (CA184-043) reported grade 3/4 toxicity in 26% versus 3% in patients treated with radiation followed by ipilimumab or placebo respectively, consistent with reported toxicity from ipilimumab alone.⁵⁸ In a phase I study of 35 patients treated with Ipilimumab and SBRT (50 Gy in 4 fractions), 2 patients treated with concurrent SBRT and ipilimumab developed dose limiting toxicity (grade 3 pancreatitis and lipase elevation); one patient with sequential ipilimumab and SBRT developed grade 3 increase in bilirubin and AST, and 12 of 35 patients (34%) had grade 3 toxicity (colitis in 4), slightly higher than reported grade 3 toxicity post ipilimumab alone (10 – 28%) with no grade 4 or 5 toxicity observed.⁵⁹ Clinical benefit was associated with increased peripheral CD8+ T cells, CD8+/CD4+ T cell ratio and proportion of CD8+ T cells expressing 4-1BB and PD-1. There was greater T cell activation in patients receiving liver SBRT versus lung SBRT. Another small study of ipilimumab with SBRT in metastatic melanoma reported responses in 6 of 22 evaluable patients, and manageable toxicity with only 3 patients discontinuing treatment due to adverse events, and grade 3/4 toxicity in 14% of patients.⁶⁰

In summary, there has not been a clear indication that toxicity is increased with the combination of

radiation and ICI, but there is a need for prospective data, especially in HCC.

2.3 Rationale

As discussed above, there is significant interest in using immune checkpoint inhibitors in the treatment of hepatocellular carcinoma. In addition, the use of SBRT has shown promise in treating subjects with hepatocellular carcinoma.

The combination of SBRT and immune checkpoint inhibition with pembrolizumab aims to capitalize on the local control effect of the radiotherapy by combining with a systemically-active agent to increase local response within the radiation field and control disease not encompassed by SBRT.

Objective response rate has been chosen as the primary outcome measure for this study. Although overall survival (OS) is the gold standard for measuring efficacy of cancer treatment, measurement of radiographic response rate is considered an acceptable endpoint for phase II clinical trials, as an effective treatment is considered likely to result in a reduction in tumor size.⁶¹ The use of RECIST 1.1 in HCC has been problematic in subjects treated with anti-angiogenic therapy such as sorafenib, or treatments involving vessel embolization (transarterial chemo-embolization, transarterial radio-embolization, or bland embolization) but both PD-1 checkpoint inhibitors and SBRT have separately been associated with RECIST responses.^{24,34} iRECIST adapts RECIST to account for unique response kinetics seen following immunotherapy, by allowing for treatment beyond unconfirmed progression (iUPD) in clinically stable patients, where there after a response may be seen. New lesions are not counted as the sum of measurement (SOM), but are recorded separately and may be considered iUPD until confirmatory progression (iCPD) This is explained in further detail in Section 11.1.4.

The selection of overall response rate includes the lesions treated with SBRT as well as systemic disease not included in the radiation volume. This composite response aims to evaluate the effect of the “treatment package” of pembrolizumab and SBRT, a paradigm in which the SBRT provides high rates of local control in the liver and the pembrolizumab controls systemic disease, and there is potential synergy and/or abscopal effect of using the two in combination. Assessment of response will be performed by a radiologist independent to the conduct of the study. Secondary endpoints will aim to measure the response in tumor lesions outside the SBRT field, an assessment of the abscopal effect described following radiotherapy. Additional secondary efficacy endpoints will include PFS and OS.

2.4 Correlative Studies Background

2.4.1 Correlation between tumor genomic characteristics and response to therapy

Introduction: Immune checkpoint inhibitors (ICIs) are an important novel class of anti-neoplastic agent that may act synergistically with radiation. Biomarkers predicting response to immune checkpoint inhibition and to the potential abscopal effect when combined with radiation are lacking. Thus, to benefit future subjects, we will seek to define novel predictive biomarkers of response. This will require a mandatory biopsy, consisting of 4 x core biopsies and blood samples to support genomic and immune correlative analyses.

These will include but are not limited to:

Germline (blood) and tumor genomic analyses

This research will evaluate whether genetic variation within a clinical trial population correlates with response to the combination treatment under evaluation. If genetic variation is found to predict efficacy or adverse events, the data might inform optimal use of therapies in the subject population. Furthermore, it is important to evaluate germline DNA variation across the genome in order to interpret tumor-specific DNA mutations.

Next generation sequencing, has provided scientists the opportunity to identify tumor-specific DNA changes (i.e., mutations, methylation status, microsatellite instability etc.), mutational loads and specific genomic signatures that may influence response to ICIs, and also to SBRT. Pembrolizumab induces a response in tumors that likely reflects an inflamed/immune phenotype. Specific immune-related gene sets (such as those capturing interferon-gamma transcriptional pathways) may be evaluated and new signatures may be identified. Tumor DNA and RNA will be extracted from biopsies at diagnosis and banked for planned whole exome sequencing (WES) and whole transcriptome gene expression analysis by RNA sequencing. In patients consenting for a repeat biopsy at 3-6 weeks, tumor specimens will also be banked. This will be offered only when deemed safe by the PI. Specific signatures detected may inform responsiveness or resistance to ICIs, and using data from RNAseq it will be possible to evaluate gene signatures previously shown to be potentially predictive of response to pembrolizumab.^{62,63}

Blood analyses

The analysis of circulating tumor DNA (ctDNA) appears to be feasible in early studies in HCC, and correlations of ctDNA may provide important insight into the timelines of response or non-response to immunotherapy and combination treatment.⁶⁴ Circulating tumor DNA (ctDNA) will be measured at diagnosis, during SBRT, at 12 weeks and at time of disease progression (20ml per time point). The absolute concentration of ctDNA within peripheral blood plasma will be calculated from the aggregated tumor-specific reads and normalized to the total concentration of cell-free (cf) DNA. At these time points DNA methylation profiles in cfDNA will also be evaluated. Samples of cfDNA will be stored at -80C, to allow for potential future post-hoc quantitative analyses.

PD-L1 Expression and Immunoscore

Tumor samples from this study will be analyzed for percentage PD-L1 expression. PD-L1 protein level, as assessed by IHC in tumor sections, has been shown to correlate with response to pembrolizumab in subjects with NSCLC, and a PD-L1 IHC diagnostic is marketed for use with pembrolizumab in NSCLC. Preliminary data indicates that this association may also be true in additional cancer types (i.e., triple-negative breast cancer, head and neck, and gastric). The burden of tumor infiltrating lymphocytes (TILs) may also predict response to ICIs and provide an 'immunoscore' which can prognosticate in HCC; densities of CD8, CD3, CD45R0 and PD-1 may also be assessed.^{65,66}

Cytokine analysis

Predictors of the abscopal effect are of great interest but lacking. Documented rises in antibodies to melanoma specific tumor antigens have been reported and in HCC this the abscopal effect has correlated with a rise in TNF-alpha.^{44,50,53} Banked samples may be analyzed using electrochemiluminescence assays for dynamic changes in cytokines of interest as a biomarker predictive of the abscopal effect. These markers will be compared to gene expression profiles and mutational signatures ascertained from tissue analysis.

Imaging

Diagnostic and radiation therapy imaging will also be investigated to explore whether imaging features are associated with molecular biomarkers or clinical outcomes.

2.4.2 Optional future biomedical research

As much remains unknown about genetic signatures and biomarkers in relation to disease response, any remaining samples from consenting patients will be banked for future biomedical research in order to give investigators the ability to further probe any notable results found during protocol-defined correlative research.

3. SUBJECT SELECTION

3.1 Inclusion Criteria

In order to be eligible for participation in this trial, the subject must:

- 3.1.1 Be willing and able to provide written informed consent/assent for the trial.
- 3.1.2 Be ≥ 18 years of age on day of signing informed consent.
- 3.1.3 Have a histologically or cytologically confirmed diagnosis of hepatocellular carcinoma, and at least one measurable lesion as defined by RECIST 1.1/iRECIST. Otherwise eligible subjects, with a radiographic diagnosis of HCC, may be enrolled for screening, but histological confirmation is mandatory prior to initiation of study therapy.
- 3.1.4 Have current liver function meeting Child Pugh Class A (5-6 points), with no encephalopathy or ascites. Child Pugh status must be calculated based on clinical and laboratory results during the screening period.
- 3.1.5 Have intrahepatic HCC amenable to SBRT:
 - maximum 10 lesions to be treated, and
 - total tumor diameter to be treated <20 cm
 - No single liver tumor >15 cm in diameter
 - No evidence of common or main branch bile duct invasion
 - No evidence of direct tumor extension into stomach, duodenum, small bowel, large bowel or diaphragm
 - Smaller satellites of HCC or non-definite HCC need not be encompassed within SBRT volumes if needed to respect normal tissue limits.
- 3.1.6 Be willing to provide tissue from a newly obtained core or excisional biopsy of a tumor lesion. Newly-obtained is defined as a specimen obtained up to 6 weeks (42 days) prior to initiation of treatment on Day 1. The subject must have a site of disease amenable to biopsy, and be a candidate for tumor biopsy. In addition, the subject must be willing to give blood for correlative studies, and have no contraindications to this.
- 3.1.7 Have a performance status of 0 or 1 on the ECOG Performance Scale.

3.1.8 Have demonstrated disease progression, after previous treatment with sorafenib or lenvatinib for advanced or metastatic disease, lasting a minimum of 8 week period, allowing for appropriate interruptions and dose reductions (i.e. second-line systemic therapy for advanced disease after failing 1st line tyrosine kinase inhibitor (TKI)). Individuals who have discontinued sorafenib/lenvatinib for documented grade 3 or 4 toxicity may be eligible for participation, provided disease progression has been observed since discontinuation of sorafenib/lenvatinib. Occasional subject may have been switched from sorafenib to lenvatinib early before progression due to intolerance and then at progression can be considered eligible having had 1 line of TKI to progression.

3.1.9 Have recovered (to \leq grade 1) from prior toxicities related to previous treatments at the time of study enrollment, with the exception of alopecia or skin depigmentation.

3.1.10 Be tested for Hepatitis B-Virus surface antigen (HbsAg) status. HBV DNA is not mandated for subjects tested negative for Hepatitis B Virus. Subjects may be included in the study if they have adequately controlled hepatitis B, defined by:

- receiving a nucleoside analog anti-viral drug for 4 or more weeks, and
- serum hepatitis B virus (HBV) DNA level of less than 100 IU/ml via polymerase chain reaction quantification assays prior to enrollment.
- in the case of subjects with known suppressed HBV viral DNA (<100 IU/ml) within 3 months prior to study entry, 7 days nucleoside analog anti-viral drug prior to study inclusion is acceptable.

3.1.11 Be tested for Hepatitis C-Virus antibody (Anti-HCV) status. Subjects with HCV infection (as characterized by the presence of detectable HCV ribonucleic acid (RNA) or anti-HCV antibody) are allowed on study. In addition, subjects with successful HCV treatment (defined as sustained virologic response [SVR] 12 or SVR 24) are allowed as long as 4 weeks have passed between completion of HCV therapy and start of study treatment. HCV RNA is not mandated for subjects tested negative for Anti-HCV during screening.

3.1.12 Demonstrate adequate organ function as defined in Table 1, all screening labs should be performed within 14 days of treatment initiation.

Table 1: Adequate Organ Function Laboratory Values

System	Laboratory Value
Hematological	
Absolute neutrophil count (ANC)	$\geq 1,200 / \text{mcL}$
Platelets	$\geq 50,000 / \text{mcL}$
Hemoglobin	$\geq 8 \text{ g/dL}$ without transfusion or EPO dependency (within 7 days of assessment)
Renal	
Serum creatinine OR Measured or calculated ^a creatinine clearance (GFR can also be used in place of creatinine or CrCl)	$\leq 1.5 \times$ upper limit of normal (ULN) OR $\geq 50 \text{ mL/min}$ for subject with creatinine levels $> 1.5 \times$ institutional ULN
Hepatic	
Serum total bilirubin	$\leq 34 \text{ umol/l}$
AST (SGOT) and ALT (SGPT)	$\leq 5 \times$ ULN

Albumin	≥ 25 g/L
Coagulation	
International Normalized Ratio (INR) or Prothrombin Time (PT)	≤ 1.5 X ULN unless subject is receiving anticoagulant therapy as long as PT or PTT is within therapeutic range of intended use of anticoagulants
Activated Partial Thromboplastin Time (aPTT)	≤ 1.5 X ULN unless subject is receiving anticoagulant therapy as long as PT or PTT is within therapeutic range of intended use of anticoagulants

^aCreatinine clearance should be calculated per institutional standard.

3.1.13 Women of child-producing potential must agree to use effective contraceptive methods prior to study entry, during study participation, and for at least 30 days after the last administration of study medication. A serum pregnancy test within 72 hours prior to the initiation of therapy will be required for women of childbearing potential. Men treated or enrolled on this trial must agree to use adequate contraception prior to and for 4 months after completion of pembrolizumab administration.

Highly effective contraception methods include:

- Total abstinence when this is in line with the preferred and usual lifestyle of the subject. Periodic abstinence (e.g., calendar, ovulation, symptothermal, post-ovulation methods) and withdrawal are not acceptable methods of contraception
- Male or Female sterilization (have had surgical bilateral oophorectomy with or without hysterectomy) or tubal ligation at least six weeks before taking study treatment. In case of oophorectomy alone, only when the reproductive status of the woman has been confirmed by follow up hormone level assessment
- Male sterilization (at least 6 months prior to screening). For female subjects on the study the vasectomized male partner should be the sole partner for that subject.
- Combination of any two of the following (a+b or a+c, or b+c):
 - a. Use of oral, injected or implanted hormonal methods of contraception or other forms of hormonal contraception that have comparable efficacy (failure rate <1%), for example hormone vaginal ring or transdermal hormone contraception
 - b. Placement of an intrauterine device (IUD) or intrauterine system (IUS)
 - c. Barrier methods of contraception: condom or occlusive cap (diaphragm or cervical/vault caps) with spermicidal foam/gel/film/cream/vaginal suppository

In case of use of oral contraception women should have been stable on the same pill for a minimum of 3 months before taking study treatment.

Note: Female subjects of childbearing age are defined as follows:

- Subjects with regular menses
- Subjects, after menarche with amenorrhea, irregular cycles, or using a contraceptive method that precludes withdrawal bleeding
- Women who have had tubal ligation

Female subjects may be considered to NOT be of childbearing potential for the following reasons:

- The subject has undergone total abdominal hysterectomy with bilateral salpingo-oophorectomy or bilateral oophorectomy
- The subject is medically confirmed to be menopausal (no menstrual period) for 24 consecutive months
- Pre-pubertal females. The parent or guardian of young female subjects who have not yet started menstruation should verify that menstruation has not begun. If a young female subject reaches menarche during the study, then she is to be considered as a woman of childbearing potential from that time forward.

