- 3.2.13. Has a known history of prior invasive malignancy except if the subject has undergone curative-intent therapy with no evidence of disease recurrence for 2 years prior to study entry. Exceptions include basal cell carcinoma of the skin, squamous cell carcinoma of the skin, superficial bladder cancer, low-risk prostate cancer or in situ cervical cancer.
- 3.2.14. Has known active central nervous system (CNS) metastases and/or carcinomatous meningitis. Subjects with previously treated brain metastases may participate provided they are stable (without evidence of progression by imaging for at least four weeks prior to the first dose of trial treatment and any neurologic symptoms have returned to baseline), have no evidence of new or enlarging brain metastases, and are not using steroids for at least 7 days prior to trial treatment. This exception does not include carcinomatous meningitis which is excluded regardless of clinical stability.
- 3.2.15. Has active autoimmune disease that has required systemic treatment in the past 2 years (i.e. with use of disease modifying agents, corticosteroids or immunosuppressive drugs). Replacement therapy (e.g. thyroxine, insulin, or physiologic corticosteroid replacement therapy at a dose of \leq 10 mg/day of prednisone or equivalent) is not considered a form of systemic treatment.
- 3.2.16. Has known history of, or any evidence of active, non-infectious pneumonitis/interstitial lung disease.
- 3.2.17. Has an active infection requiring systemic therapy.
- 3.2.18. Has a history or current evidence of any condition, therapy, or laboratory abnormality that might confound the results of the trial, interfere with the subject's participation for the full duration of the trial, or is not in the best interest of the subject to participate, in the opinion of the treating investigator.
- 3.2.19. Has known psychiatric or substance abuse disorders that would interfere with cooperation with the requirements of the trial.
- 3.2.20. Is pregnant or breastfeeding, or expecting to conceive or father children within the projected duration of the trial, starting with the pre-screening or screening visit through 120 days after the last dose of trial treatment.

- 3.2.21. Has received prior therapy with an anti-PD-1, anti-PD-L1, or anti-PD-L2 agent.
- 3.2.22. Has a known history of Human Immunodeficiency Virus (HIV) (HIV 1/2 antibodies).
- 3.2.23. Has alcohol related or non-alcoholic steatohepatitis (NASH) related cirrhosis.

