5.1.1.1 Timing of Dose Administration

Trial treatment should be administered on Day 1 of each cycle after all procedures/assessments have been completed as detailed in the STUDY CALENDAR (Section 10). Trial treatment may be administered up to 1 day before or 3 days after the scheduled Day 1 of each cycle due to administrative reasons.

All trial treatments will be administered on an outpatient basis.

In general, toxicities from previous cycles of treatment should have returned to Grade 0-1 before the next dose of study medication (see Section 6.1 for specific guidance). Pre-existing Grade 2 toxicities, which did not result in exclusion from the trial, (for example, liver transaminase abnormalities) should be stable.

Pembrolizumab 200 mg will be administered as a 30 minute IV infusion every 3 weeks. Every effort should be made to target infusion timing to be as close to 30 minutes as possible. However, given the variability of infusion pumps from site to site, a window of -5 minutes and +10 minutes is permitted (i.e., infusion time is 30 minutes: -5 min/+10 min).

The Pharmacy Manual contains specific instructions for the preparation of the pembrolizumab infusion fluid and administration of infusion solution.

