5.3.1 Retreatment with Pembrolizumab

Subjects who stop pembrolizumab with SD/iSD or better may be eligible for up to one year of additional pembrolizumab therapy if they progress after stopping study treatment. This retreatment is termed the Second Course Phase of this study and is only available if the study remains open (accrual may be completed, but patients still in follow-up) and the subject meets the following conditions:

Either

- Stopped initial treatment with pembrolizumab after attaining an investigator-determined confirmed CR/iCR according to RECIST 1.1/iRECIST, and
 - Was treated for at least 24 weeks with pembrolizumab before discontinuing therapy
 - Received at least two treatments with pembrolizumab beyond the date when the initial CR/iCR was declared

OR

- Had SD/iSD, PR/iPR or CR/iCR and stopped pembrolizumab treatment after 24 months of study therapy for reasons other than disease progression or intolerance

AND

- Experienced an investigator-determined confirmed radiographic disease progression after stopping their initial treatment with pembrolizumab

- Did not receive any anti-cancer treatment since the last dose of pembrolizumab, except for SBRT to oligopressive lesion (see Section 5.3.2)
- Has ECOG performance status of 0 or 1
- Demonstrates adequate organ function as listed in Inclusion Criteria (Section 3.1)
- Female subjects of childbearing potential should have a negative serum or urine pregnancy test within 72 hours prior to receiving retreatment with study medication.
- Female subjects of childbearing potential should be willing to use 2 methods of birth control or be surgically sterile, or abstain from heterosexual activity for the course of the study through 120 days after the last dose of study medication. Subjects of child bearing potential are those who have not been surgically sterilized or have been free from menses for > 1 year.
- Male subjects should agree to use an adequate method of contraception starting with the first dose of study therapy through 120 days after the last dose of study therapy.
- Does not have a history or current evidence of any condition, therapy, or laboratory abnormality that might interfere with the subject's participation for the full duration of the trial or is not in the best interest of the subject to participate, in the opinion of the treating investigator.

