Subjects who restart treatment will be retreated at the same dose and dose interval as when they last received pembrolizumab. Treatment will be administered for up to one additional year.

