7.7 Pregnancy

If the study subject is the father, then two forms should be completed, one for the father and the other for the mother and neonate. To ensure subject safety each pregnancy must also be reported to Merck within 15 days of learning of its occurrence.

Pregnancies and lactations that occur in a study subject or in a study subject's partner from the time of treatment allocation through 120 days following cessation of study treatment, or 30 days following cessation of treatment if the subject initiates new anticancer therapy, whichever is earlier, must be reported by the investigator to the Central Office within 24 hours of learning of the event. Central Office will report pregnancy to Merck Global Safety. (Attn: Worldwide Product Safety; [contact]) within 2 working days. All reported pregnancies must be followed up to determine outcome, including

spontaneous or voluntary termination, details of birth, and the presence or absence of any birth defects, congenital abnormalities or maternal and newborn complications.

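### Section 3.1.13 sets a 30-day post-dose contraception minimum for women, while Section 5.3.1 requires 120 days for the same drug and dose: a gap of up to 90 days

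*Combined protocol and SAP*

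**What the plan says.** The protocol gives a contraception period after the last dose in two places.

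- **First course, women (Section 3.1.13).** Contraception is required before entry, during participation, and "for at least 30 days after the last administration of study medication".
- **First course, men (Section 3.1.13).** Contraception is required before and "for 4 months after completion of pembrolizumab administration".
- **Second Course, women (Section 5.3.1).** A woman of childbearing potential must use two methods, be surgically sterile, or "abstain from heterosexual activity for the course of the study through 120 days after the last dose of study medication".
- **Second Course, men (Section 5.3.1).** Men must use "contraception starting with the first dose of study therapy through 120 days after the last dose of study therapy".

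The treatment is the same in both courses. Section 5.1.1.1 states: "Pembrolizumab 200 mg will be administered as a 30 minute IV infusion every 3 weeks". Section 5.3.1 states: "Subjects who restart treatment will be retreated at the same dose and dose interval as when they last received pembrolizumab".

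Two other provisions bear on the same period. Exclusion 3.2.20 bars anyone who expects to conceive or father a child in the window "starting with the pre-screening or screening visit through 120 days after the last dose of trial treatment". Section 7.7 requires pregnancies to be reported for 120 days after treatment stops, or "30 days following cessation of treatment if the subject initiates new anticancer therapy, whichever is earlier".

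**The concern.** Two rules with the same purpose, for the same drug at the same dose and interval, give women different minimum periods. The protocol gives no reason for the shorter one. Exposure does not supply a reason: the first course may run for 24 months or 35 administrations, whichever is later (Section 5.3), and includes SBRT, while the Second Course is limited to one year.

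A woman can follow 3.1.13 to the letter, stop contraception at day 30, and conceive between days 31 and 120. In that same interval a retreated woman must prevent conception, and a woman planning to conceive would not have been enrolled. Site staff counselling a first-course participant would find 30 days in one section and 120 days in three others. The matter is participant safety and consistency of the protocol. It has no bearing on the statistical design.

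**Working it through.** No design figure is involved, so the check compares the stated periods directly.

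| Provision | Who | Period after last dose |
|---|---|---|
| 3.1.13, first course | Women | at least 30 days |
| 5.3.1, Second Course | Women | 120 days |
| 3.1.13, first course | Men | 4 months |
| 5.3.1, Second Course | Men | 120 days |
| 3.2.20, intent at entry | Both sexes | 120 days |
| 7.7, pregnancy reporting | Participants and partners | 120 days, or 30 days if new anticancer therapy starts, whichever is earlier |

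1. **Women, Second Course minus first course.** 120 − 30 = 90 days. Because 3.1.13 sets a floor, 90 days is the largest gap. It applies to a woman who stops at the minimum.
2. **Men, first course against Second Course.** Taking a month as 30 days, 4 × 30 = 120 days, a difference of 0. Taking an average calendar month, 4 × 365.25 / 12 = 121.75 days, a difference of 1.75 days. The men's periods agree.
3. **Is there another 30-day figure that would support 3.1.13?** The only one in a pregnancy provision is in Section 7.7. It shortens a reporting window when new anticancer therapy begins. Section 3.1.13 carries no such condition, so 7.7 neither explains its 30 days nor conflicts with it.
4. **Does 3.2.20 fill the gap?** It screens for the intention to conceive at entry. It does not require contraception on days 31 to 120, so unplanned conception remains.
5. **How many could be affected?** The number of women of childbearing potential is not given. The only upper bound is the planned accrual of 27 (Section 13.2); the true number is smaller and could be zero.
6. **After correction.** With 120 days in 3.1.13, the gap is 120 − 120 = 0 days. The section then matches 5.3.1, 3.2.20 and the main window in 7.7, and agrees with the men's period to within 1.75 days.

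**The case against.** The strongest objection is that 3.1.13 also requires contraception during study participation. Section 5.5 ends study membership only at death, withdrawal of consent, loss to follow-up or termination of the study, and survival follow-up under 5.4 runs until death. On that reading a woman in follow-up is still participating and may not stop at day 30. The 30-day clause would still have a use, because it would bind a woman who withdraws soon after a dose. The phrase is therefore not free of ambiguity. However, Table 6 in Section 5.4 speaks of removal from study when it means coming off treatment, and the serious adverse event rule in Section 7.2 treats participation as something that stops, with a four-week reporting period after it. A duty to use contraception until death is also implausible as the intended meaning. The natural reading remains a 30-day minimum after the last dose.

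Second, the two rules apply to different phases: one is an entry criterion, the other a condition for optional retreatment. No woman receives both instructions for the same last dose, and 120 days satisfies a minimum of 30. This is correct, and it means the two rules can both be obeyed. It does not explain why the same dose and interval should carry a fourfold difference (120 / 30 = 4) for women and essentially none for men.

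Third, the protocol contains no half-life or reproductive-toxicity argument for either figure, and the Investigator's Brochure and consent form are not available here. This stands. The documents show that 30 days is the outlier; they do not show by themselves that conception after day 30 is harmful. The consent form may already say 120 days.

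Fourth, few women are affected and those planning pregnancy are excluded. This also stands, and it limits the importance of the point without removing it.

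**Conclusion.** The point holds. The first-course minimum for women is 30 days where the protocol's own standard, in every comparable provision, is 120 days or about 120 days. The gap is up to 90 days, and it matters only for unplanned conception among a small, unstated number of women within an accrual of at most 27. The conclusion rests on two readings: that participation in 3.1.13 does not extend through survival follow-up, and that 120 days is the intended figure because the other provisions agree on it. Neither needs an outside source. The correction should be made because it is simple and fetal exposure could not be undone.

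**What to change.** In Section 3.1.13, replace the 30-day minimum for women with at least 120 days after the last administration of study medication. Sections 3.2.20, 5.3.1 and 7.7 need no change. Check the consent form and, if it repeats 30 days, bring it into line.

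The cost is one line of protocol text, the consent check, and informing any enrolled woman of childbearing potential who is on treatment or within 120 days of her last dose. The burden on participants is a commitment up to 90 days longer for the few women concerned, matching what retreated women must already do and, to within two days, what is asked of men.
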